6. PROTOCOL

I. Study Overview and Specific Aims

The proposed multi-center, open-label, longitudinal cohort study aims to capture the safety profile of FMT in recurrent CDI, as well as to contribute additional efficacy data to the existing body of evidence. The proposed study includes collaboration with Investigators who are able to define the microbial landscape of patients pre- and post-FMT, and further elucidate if there is a microbial signature that predisposes patients to respond, fail treatment, or have adverse events from FMT.

Study Title

Safety of fecal microbiota **T**ransplantation: **O**penBiome **O**utcomes and **L**ongitudinal follow-up (STOOL) for recurrent *Clostridium difficile* infection

Specific aims (SA)

SA1. Determine the short-term (<6 weeks) safety of FMT for the prevention of further CDI recurrence.

Hypothesis: Careful donor screening for both infectious and non-infectious yet potentially microbiome-associated conditions minimize the risk of donor to recipient transmission of disease. Therefore, FMT will not be associated with meaningful number of *related* serious adverse events, recognizing that the recurrent CDI patient population is conventionally elderly with multiple comorbidities and may be at risk for FMT procedure-related complications compared to otherwise young and healthy individuals based on conventional literature.

SA2. Determine the long-term (6-12 months) safety of FMT for the prevention of further CDI recurrence.

Hypothesis: Careful donor screening for both infectious and non-infectious yet potentially microbiome-associated conditions minimize the risk of donor to recipient transmission of disease. Therefore, FMT will not be associated with meaningful number of *related* serious adverse events, recognizing that the recurrent CDI patient population is conventionally elderly with multiple comorbidities and may be at risk for developing new conditions, new medications or adverse events including death, but unrelated to FMT material.

SA3. Determine the longitudinal robustness of FMT clinical cure rate for the prevention of further CDI recurrence.

Hypothesis: We predict a clinical cure rate in keeping with the current literature (80-90%) at the12 month follow-up time interval. This predicted longitudinal response rate would exclude patients who require further antibiotics that put them at risk for CDI reinfection, not true recurrence.

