1. Colonoscopy/sigmoidoscopy: If patients experience clinical non-response and require vancomycin/fidaxomicin within 6 weeks post-FMT, after a 10 day course subject may opt to undergo a second FMT via colonoscopy with an alternate donor at the physician's discretion. Subjects will be followed per protocol for duration of study.

2. Enema: If patients experience clinical non-response and require vancomycin/fidaxomicin within 6 weeks post-FMT, after a 10 day course subject may opt to undergo a second FMT via colonoscopy with an alternate donor at the physician's. Subjects will be followed per protocol for duration of study.

Withdrawal

- 1. All reasons for study withdrawal will be reported.
- 2. Classification of withdrawal:
 - Post-enrollment but pre-FMT
 - Post-FMT but lost to follow-up at:
 - o Day 3
 - o Week 6
 - o Month 6
 - \circ Month 12
 - All reasonable efforts will be exhausted to contact subjects, and data analysis will be based on the last available assessment.
 - Adverse event or serious adverse event mediating withdrawal
 - Rescind informed consent
 - Procedure-related ineligible patients
 - Patients undergoing colonoscopy/sigmoidoscopy and discovered to be ineligible due to newly discovered exclusionary criteria (eg. in-situ colorectal cancer). FMT will not be performed as part of this study and no data will be collected.

V. Study Observations and Measurements

Study Endpoints

Safety Endpoints

Safety will be assessed by short and long-term safety summaries classified into:

- 1. Serious Adverse Events (SAE)
- 2. Adverse Events (AE)
- 3. New medical conditions
- 4. Changes in pre-existing medical conditions

Efficacy Endpoints

Efficacy will be captured through:

- 1. Clinical cure rate of first FMT at 6-week follow-up
 - Colonoscopy
 - Sigmoidoscopy
 - Enema

2. Clinical cure rate of second FMT at 6-week follow-up, in patients with clinical non-response

- Colonoscopy/sigmoidoscopy non-response: Alternate donor FMT by colonoscopy
- Enema non-response: Alternate donor FMT by colonoscopy

Microbiome Endpoints

Sequencing data targeting the composition of the gut microbiome will be used to assess whether there are consistent microbial signatures associated with clinical cure, clinical non-response, or safety endpoints.

Data Collection

Case Report Forms will be utilized to capture and collect data (Appendix 4):

1. Baseline Assessment (Day 0 - Clinical Assessment)

Section 1: Clinical Evaluation

- Study patient identifier
- Date

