- Demographics: Age, sex, race/ethnicity
- Pre-existing medical conditions
- Concomitant medications
- Vital signs including height, weight, calculated body mass index (BMI)
- CDI History, including:
 - o Date of initial CDI diagnosis
 - Number of CDI recurrences since initial diagnosis
 - o Baseline clinical symptoms and severity related to CDI
 - CDI treatments received to date

Section 2: FMT Procedure

- Study patient identifier
- Date
- Description of FMT procedures, including:
 - Route of administration (colonoscopy/sigmoidoscopy or enema)
 - Location in colon where FMT delivered
 - Sedation (if applicable)
 - Prep quality (if applicable)
 - Findings of colonoscopy (if applicable)
- Dose
- Unit ID/Lot# of each treatment
- Expiration Date
- Storage Condition
- FMT retention time (if less than 1 hour)
- Immediate adverse events

2. Short-term assessment I (Day 3 – Telephone Assessment)

- Study patient identifier
- Date
- Any change in baseline clinical symptoms related to CDI
- Assessment of SAEs, including:
 - Any complications related to FMT administration
 - Any potential infectious complications such as transmissible enteric infections, sepsis, peritonitis, or bacteremia
 - Any non-serious newly diagnosed infections (specific organism and body site)

- Any new medical conditions / new medications with associated clinical course
- Any changes in pre-existing medical conditions with associated clinical course
- 3. Short-term assessment II (Week 6 Clinical Assessment)
 - Study patient identifier
 - Date
 - Vital signs including height, weight, calculated body mass index (BMI)
 - Any change in baseline clinical symptoms related to CDI including documentation of clinical cure or clinical non-response
 - Assessment of SAEs, including:
 - Any complications related to FMT administration
 - Any potential infectious complications such as transmissible enteric infections, sepsis, peritonitis, or bacteremia.
 - Any new non-serious diagnosed infections (specific organism and body site)
 - Any new medical conditions / new medications with associated clinical course
 - Any changes in pre-existing medical conditions with associated clinical course

4. Long-term assessment I (Month 6 – Telephone Assessment)

- Study patient identifier
- Date
- Self-reported height and weight, resulting calculated BMI
- Any recurrence of CDI with description of clinical course, including additional treatments received
- Assessment of any new SAEs

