1. FMT procedure-related adverse events from colonoscopy/sigmoidoscopy or enema (e.g. perforation, sedation related)

2. FMT material-related adverse events (e.g. transmissible infection, allergic reaction) 3. Short-term safety: Both solicited and unsolicited adverse events will be recorded by, telephone follow-up at Day 3 (+/- 2 days) and clinical assessment at Week 6 (+/- 2 weeks).

4. Long-term safety evaluations will focus on any new medical conditions/medications, which may be related or unrelated to FMT. This information will be elicited at the 6 month and 12 month follow-up telephone call and documented.

VI-A. Adverse Events Reporting

A. Definitions

1. Adverse Event (AE)

An AE is any untoward medical occurrence in a patient or study subject administered FMT that does not necessarily have a causal relationship with this treatment. An AE can therefore be any unfavorable and unintended sign (including an abnormal laboratory finding), symptom, or disease temporally associated with the use of a FMT, whether or not related to the FMT.

• AEs may be new events or may be pre-existing conditions that have become aggravated or have worsened in severity or frequency.

• AEs may be clinically significant changes from baseline in physical examination, laboratory tests, or other diagnostic investigation (e.g. laboratory results, radiographic findings).

Pregnancy is not an AE; however, if a female subject becomes pregnant during the conduct of the study, the Investigator will notify Sponsor who is responsible for notifying the FDA.

2. Serious Adverse Event (SAE)

A serious adverse event is any adverse experience occurring during or after FMT that results in any of the following outcomes:

• Death

• Life-threatening experience

Note: An adverse event or suspected adverse reaction is considered "life-threatening" if, in the view of either the Investigator or Sponsor, its occurrence places the patient or subject at immediate risk of death. It does not include an adverse event or suspected adverse reaction that, had it occurred in a more severe form, might have caused death.

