• Requires inpatient hospitalization or prolongation of existing hospitalization Note: Adverse events requiring hospital admissions that are less than 24 hours in duration do not meet this criterion. A scheduled hospitalization for a pre-existing condition that has not worsened during participation in the study does not meet this criterion. Pre-planned hospitalizations for an elective medical/surgical procedure or routine check-ups do not meet this criterion. Admission for CDI relapse will not be included in this definition.

- Results in persistent or significant disability or incapacity
- Results in a congenital anomaly or birth defect

• Results in an important medical event

Note: Important medical events are those that may not be immediately life threatening or result in death or hospitalization but may jeopardize the patient or may require intervention to prevent one of the outcomes listed in the definition above.

3. Planned Hospitalization

A hospitalization planned prior to FMT is to be considered a therapeutic intervention and not the result of a new SAE. If the hospitalization or procedure is executed as planned, it will be recorded in the subject's medical history or procedures. However, if the event/condition worsens during the study, it must be reported as an AE.

4. Adverse reaction

An adverse reaction means any adverse event caused by FMT. Adverse reactions are a subset of all suspected adverse events for which there is reason to conclude that FMT caused the event.

5. Suspected Adverse Reaction

Suspected adverse reaction means any adverse event for which there is a reasonable possibility that FMT caused the adverse event. For the purposes of IND safety reporting, 'reasonable possibility' means there is evidence to suggest a causal relationship between FMT and the adverse event. A suspected adverse reaction implies a lesser degree of certainty about causality than adverse reaction, which means any adverse event caused by a therapy.

6. Unexpected

An adverse event or suspected adverse reaction is considered "unexpected" if it is not listed in the Investigator brochure or is not listed at the specificity or severity that has been observed; or is not consistent with the risk information described in the general investigational plan or elsewhere in the current application.

VI-B. Solicited Adverse Events

Short-term

The following short-term AEs and their associated intensities will be solicited:

- Fever
 - Mild 37.7-38.6°C

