• The AE is more likely explained by FMT than by another cause

VI-E. Reporting Safety Observations by the Investigator to the Sponsor

1. Reporting of Non-serious AEs

All AEs, regardless of seriousness, severity, or causal relationship to FMT, will be recorded in the AE section of the subject case report form.

2. Reporting of FMT Exposure during Pregnancy

If a female subject or the female partner of a male subject becomes pregnant during the course of study, the Investigator must report this occurrence to the Sponsor within **72 hours** of becoming aware of the pregnancy. The Investigator is required to follow up on the pregnancy until it has completed. The outcome of the pregnancy and the status of the newborn (if applicable) will be reported within 24 hours of becoming aware. If the female partner of a male subject becomes pregnant, the Investigator must obtain consent to collect pregnancy information (including the status of the newborn, if applicable).

3. Reporting of Safety Observations by the Investigator

Any occurrence of the following events or outcomes must be reported expeditiously by the Investigator or qualified designee to the local IRB and to the Sponsor, who will be responsible for reporting the event to the FDA:

- 1. SAE related to FMT material
- 2. Death of a subject related to FMT material

The site Investigator is to report any safety observations from the list above to the Sponsor within **72 hours** of becoming aware of the event, who in turn, will notify the FDA. Any observation that is also an AE will be recorded on the subjects case report form along with any actions taken. If not all information is available at the time of initial report, follow up SAE reports will be completed and submitted.

Any occurrence of the following events or outcomes must be reported by the Investigator or qualified designee to the local IRB and to the Sponsor, who will be responsible for reporting the event to the FDA:

- 1. SAE unrelated to FMT material
- 2. Death of subject unrelated to FMT material
- 3. Hospitalization related to CDI
- 4. New or worsening medical condition, or new medications

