The Investigator is to report any safety observations from the list above to the Sponsor within **7 days** of becoming aware of the event. The Sponsor will notify the FDA in its Annual Report. Any observation that is also an AE will be recorded on the subjects case report form along with any actions taken. If not all information is available at the time of initial report, follow up SAE reports will be completed and submitted.

The site Investigator is required to follow SAEs until resolution, regardless of whether the subjects are still participating in the study. Resolution is defined as:

- Resolved with or without residual effects
- Return to baseline for a pre-existing condition
- Fatal outcome; if autopsy is performed, the autopsy report must be provided to the Sponsor.

VI-F. Monitoring the study database and submitting safety reports

The Sponsor will notify FDA of any unexpected fatal or life-threatening suspected adverse reaction related to FMT material as soon as possible, but no later than 7 calendar days after the Sponsor's initial receipt of the information. The Sponsor will notify the FDA and all participating Investigators in an IND safety report of potentially serious risks from this study as soon as possible, but no later than 15 calendar days after the Sponsor receives the safety information and determines that the information qualifies for reporting. Participating Investigators include all Investigators enrolling subjects under the Sponsor's IND. In addition, the Sponsor will identify in each IND safety report, all IND safety reports previously submitted to FDA concerning a similar suspected adverse reaction and will analyze the significance of the suspected adverse reaction in light of previous, similar reports or any other relevant information. The Sponsor will evaluate a suspected adverse reaction in the context of other related reports or adverse events. The Sponsor will periodically review and analyze the entire safety database, for IND safety reporting purposes, and also to update Investigator brochures with new safety information. An IND safety report will be submitted when any of the following criteria are met:

A. Serious and unexpected suspected adverse reaction related to FMT material

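### The all-cause SAE rate omits admissions for CDI relapse that qualify only as hospitalization, and no planned safety summary shows them alongside it

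*Combined protocol and SAP*

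**What the plan says.** All references are to Section 6 (Protocol) of the combined document.

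- **SAE definition (VI-A, item 2).** Seriousness can arise through death, a life-threatening experience, hospitalization, disability, a congenital anomaly or an important medical event. The note under hospitalization removes stays shorter than 24 hours, scheduled stays and pre-planned stays, and then adds: "Admission for CDI relapse will not be included in this definition". The three preceding exclusions refer to the criterion; this one refers to the definition.
- **Endpoints (V, Study Endpoints).** "Safety will be assessed by short and long-term safety summaries classified into" four groups: SAEs, AEs, new conditions and changes in existing conditions.
- **Analysis (V, Data Analysis).** Safety endpoints are to be given as raw counts and crude rates. X (Potential Limitations, item 1) puts the emphasis on counts and rates of SAEs.
- **Notification (VI-E, item 3).** "Hospitalization related to CDI" is on the list that the investigator must send to the sponsor within 7 days. For that list, "The Sponsor will notify the FDA in its Annual Report".
- **Recording.** "AEs may be new events or may be pre-existing conditions that have become aggravated or have worsened in severity or frequency" (VI-A, item 1), and "All AEs, regardless of seriousness, severity, or causal relationship to FMT, will be recorded in the AE section of the subject case report form" (VI-E, item 1).
- **Follow-up (V, Data Collection).** Months 6 and 12 collect "Any recurrence of CDI with description of clinical course, including additional treatments received".

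**The concern.** A subject who stops antibiotics, receives FMT, relapses and spends several days in hospital has had an event that would be an SAE under the hospitalization criterion for almost any other unplanned cause. Here it is not one on that ground. The all-cause SAE rate will therefore be lower than a count of all unplanned admissions of 24 hours or more, and a reader of the results table would have no way to see by how much.

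The efficacy side does not fill the gap. Clinical non-response is defined by diarrhea plus a need for CDI antibiotics, so it carries no information on admission, and both listed cure endpoints are assessed at 6 weeks. A later relapse that leads to admission is collected at Month 6 or 12 but has no assigned place in the analysis.

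The wording adds a smaller risk. Because the sentence says *definition* where its neighbours say *criterion*, a site could apply it to a relapse that is serious on other grounds.

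**Working it through.** **No figure to reproduce.** The plan states no expected SAE rate and no admission rate after relapse, and the sample size of 150 rests on recruitment time. What follows is an illustration of size.

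**Step 1: where a relapse admission can appear in the reported results**

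| Place in the plan | Relapse admission visible as such? |
|---|---|
| SAE count, by hospitalization | No, excluded by VI-A |
| SAE count, by another seriousness criterion | Yes, if the relapse meets one |
| AE class, or changes in existing conditions | Recorded, but no line for admission |
| 6-week cure rates | Counted as non-response, mild and hospitalized alike |
| Months 6 and 12 recurrence data | Collected; no planned summary of admissions |
| 7-day notification and annual report | Yes, but as notification, not analysis |

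**Step 2: inputs**

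- N = 150 (target enrollment).
- Cure rate 80-90% (SA3, at 12 months), hence a failure share f of 0.10 to 0.20.
- h = share of failures admitted for relapse for 24 hours or more. This is an **assumption**: 10-30% as a working range, 5-50% as a wide one.

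**Step 3: expected number omitted = N × f × h**

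- Failures: 150 × 0.10 = 15; 150 × 0.20 = 30.
- Working range: 15 × 0.10 = 1.5; 30 × 0.30 = 9. As a share of the cohort: 1.5/150 = 1.0% and 9/150 = 6.0%.
- Wide range: 15 × 0.05 = 0.75; 30 × 0.50 = 15. As a share of the cohort: 0.5% and 10%.
- Chance that at least one subject is omitted, at the lowest combination: 1 − (1 − 0.10 × 0.05)^150 = 53%. At the highest combination it exceeds 99%.

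**Step 4: effect on a reported rate (illustration)**

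Suppose other SAEs occur in 15 of 150 subjects (assumed): 10.0%, exact 95% CI 5.7% to 16.0%. With f = 0.20 and h = 0.25, the expected number omitted is 150 × 0.20 × 0.25 = 7.5. Adding 8 subjects gives 23/150 = 15.3%, exact 95% CI 10.0% to 22.1%.

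These figures count subjects. Anyone admitted for relapse who also has another SAE is already in the numerator, so the subject-level gap could be smaller.

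**The case against.** The strongest reply is that this is an open and coherent design choice. SA1 and SA2 are hypotheses about *related* SAEs, recurrence belongs to SA3, and it is reasonable to keep treatment failure apart from harm while requiring separate notification of CDI hospitalizations. The causality guidance in VI-D names the disease under treatment as a possible alternative cause, so many relapse admissions would be judged unrelated. The DSMB also reviews clinical status and adverse events quarterly.

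Much of that stands. The effect falls mainly on the all-cause SAE rate, and the safety data do contain the event. It does not answer the reporting point: notification to the sponsor is not a line in a results table, and the DSMB report in VII-E is specified as a summary of AEs and SAEs without one either.

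Four stronger readings are tempting, and the documents do not support them.

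- *A CDI relapse can only ever be a non-serious AE.* The sentence sits in the note to the hospitalization bullet. Death, life-threatening experience, disability and important medical event are separate bullets, so a relapse that meets one of them can still be an SAE. The word *definition* makes this less clear than it should be, but position favours the narrow reading.
- *Relapse admission is the most likely serious outcome after a failed FMT.* This may be plausible, but no rate is given from which to rank it.
- *The exclusion lets material-related infection bypass the halting rules.* VI-G makes confirmed donor-to-subject transmission of a clinically concerning infection its own trigger for a safety review, with no SAE label needed.
- *The 12/80 (15%) SAE rate in the cited retrospective series is a benchmark.* That series is of immunocompromised patients, with events counted within 12 weeks. This trial excludes severely immunocompromised patients and follows subjects for 12 months. The application does not say whether the series counted relapse admissions.

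**Conclusion.** The point holds as a reporting gap. The all-cause SAE rate leaves out relapse admissions that qualify only as hospitalization, and no planned summary puts them back beside it.

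The size cannot be taken from the documents. It is 1 to 6 percentage points of the cohort if 10-30% of failures are admitted, and 0.5 to 10 points if 5-50% are, given the SA3 cure range at N = 150. The SA3 range also sets aside subjects who need further antibiotics and become reinfected, so it may not describe every CDI admission.

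This does not show that events are lost to the sponsor or that the related-SAE hypotheses are compromised. It is a cheap improvement worth making, because it changes a headline safety figure using data the sites already report.

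**What to change.** 1. In the hospitalization note of VI-A, item 2, replace the word *definition* with *criterion* in the sentence on CDI relapse. It is then explicit that a relapse meeting another seriousness criterion remains an SAE.
2. Add CDI-related hospitalization as a named line in the short-term and long-term safety summaries: n/150, crude rate and 95% CI.
3. Report the all-cause SAE rate with and without the excluded relapse admissions, applying the same 24-hour rule to those added so that the two rates are comparable.
4. Cross-reference VI-A, item 2, and VI-E, item 3. One speaks of relapse and the other of hospitalization related to CDI; say whether they cover the same events.

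These steps leave the rest of the SAE definition as it is. If the sponsor prefers to change the definition itself, VI-A, VI-E and the end of VI-G must be reconciled, because VI-G ties a related SAE to eligibility for a second FMT.

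**Cost.** A change of wording, one table row and one extra rate, from admissions already notified to the sponsor. The downside is a somewhat higher stated rate of serious events.
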